### b. Secondary Objectives

1. To measure the distribution of inspiratory flow rates with an InCheck Dial device set on measuring PIF using the medium low resistance setting in patients admitted with COPD exacerbations at Baylor University Medical Center, Dallas TX at the time of enrollment and day of discharge.
2. To determine the hospital length of stay for patients admitted with the diagnosis of COPD exacerbation.
3. To monitor and report any side effects from using once-daily ICS/LABA/LAMA or PRN therapy.
4. To evaluate the transition of care in delivering respiratory therapy medications from hospital to home.
5. To compare the number of PRN treatments, length of hospital stay, and rate of readmissions with findings in a previously analyzed historical cohort of 60 patients in our healthcare system.

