Results of an analysis of 60 patient charts randomly selected after hospitalization at Baylor University Medical Center for an exacerbation of underlying airways disease (>90% with COPD) showed tremendous variation in practice patterns; with 30% of patients receiving short-acting beta-antagonists and muscarinic agonists (SABA/SAMA) only, 70% receiving long-acting beta-antagonists (LABA) with PRN SABA/SAMA, and only 42% receiving a long-acting muscarinic agonist (LAMA), despite practice guidelines encouraging the use of SABA/SAMA only (typically 4 times daily and as needed).

It is this large variability that renders the evaluation and interpretation of institution-specific outcomes difficult. The main impetus for the proposed study is therefore to establish a more standardized open-label protocol which would allow for a more accurate assessment of intervention outcomes. As one of several secondary goals of this study, we aim to compare key outcomes (including, number of PRN treatments, length of hospital stay, and rate of readmission) with those from the historical cohort described above, when a combination LABA/LAMA/ICS inhaler is used as the primary scheduled daily inhaled therapy.

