#### **5.2.4 TREATMENT (Enrollment to Discharge)**

TRELEGY ELLIPTA (fluticasone furoate 100 mcg, umeclidinium 62.5 mcg, and vilanterol 25 mcg inhalation powder) will be initiated on the morning of enrollment if feasible, or the morning after enrollment otherwise. Treatment will continue daily until discharge. Treatments will be administered by a respiratory therapist daily in the morning between 06:00 AM and 12:00 PM. Patients will receive nebulized short-acting beta-2 agonist (SABA) treatments of albuterol sulfate (2.5mg) as needed during hospitalization. Patients will receive prednisone 40 mg PO daily for the first 7 days from enrollment, subtracting 1 day for each consecutive day the patient received systemic corticosteroid treatment prior to enrollment.

Treatment procedures/assessments include:

- Concomitant Medications
- AE Assessment
- TRELEGY administration

Data from the following specified assessments will be collected daily, when available, and entered the case report forms (CRFs):

- Vital Signs
- Short-acting beta agonist (SABA) therapy: number and time of treatments

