### 7.2 Disallowed Medications

Subjects will be prohibited from taking the following medications during the study:

- Inhaled short-acting muscarinic antagonist (SAMAs), such as ipratropium bromide.
- Inhaled therapies other than TRELEGY ELLIPTA containing any of the following: ICS, LAMA, or LABA.

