#### **d. Analysis of Secondary Endpoints**

Time (in days) in between PRN treatments, change in respiratory inspiratory flow rate from baseline to discharge, length of stay, at-home drug compliance, 30-day readmissions (all-cause and COPD/Asthma exacerbation), and 30-day survival will be compared between patients who were and were not readmitted using t-tests or chi-square tests (or Wilcoxon Rank Sum tests and Fisher's Exact tests), as appropriate.

The efficacy of the treatment protocol in the study cohort compared to the historical cohort will be assessed by comparing (1) the average number of PRN treatments per patient day while hospitalized estimated using a robust Poisson regression model (2) length of stay in the hospital, and (3) the rate of rehospitalization, using the Wilcoxon Rank sum test.

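### The between-cohort PRN comparison would omit any scheduled short-acting treatments given to up to 30% of the historical cohort, so the pooled ratio could read against the study regimen while total short-acting use is lower

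*Combined protocol and SAP*

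**What the plan says.** **The comparison.** Objective 5 (section 2.b) is "To compare the number of PRN treatments, length of hospital stay, and rate of readmissions with findings in a previously analyzed historical cohort"; its stated size is 60. Section 8.7.d opens with "The efficacy of the treatment protocol in the study cohort compared to the historical cohort will be assessed by comparing" and lists three measures. The first is "the average number of PRN treatments per patient day while hospitalized estimated using a robust Poisson regression model"; the other two are length of stay and rehospitalization. Scheduled short-acting treatments are not mentioned.

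**The study regimen.** The scheduled inhaled therapy is a once-daily LABA/LAMA/ICS inhaler. Section 5.2.4 adds: "Patients will receive nebulized short-acting beta-2 agonist (SABA) treatments of albuterol sulfate (2.5mg) as needed during hospitalization". Section 7.2 prohibits "Inhaled short-acting muscarinic antagonist (SAMAs), such as ipratropium bromide". Section 5.2.4 also has the number and time of SABA treatments entered on the CRF.

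**The historical regimen.** Section 3.c reports "Results of an analysis of 60 patient charts randomly selected after hospitalization at Baylor University Medical Center", "with 30% of patients receiving short-acting beta-antagonists and muscarinic agonists (SABA/SAMA) only". (The wording transposes agonist and antagonist; I read it as short-acting bronchodilators.) The other 70% are described as having a LABA with PRN SABA/SAMA. The section adds that practice varied "despite practice guidelines encouraging the use of SABA/SAMA only (typically 4 times daily and as needed").

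No section defines a PRN treatment for the historical charts, counts their scheduled short-acting doses, or splits or adjusts the comparison by historical regimen.

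**The concern.** A PRN count means different things under the two regimens. In the study it captures every short-acting treatment the protocol provides for. In a patient on scheduled short-acting therapy, it captures only what was given on top of the schedule. If some historical patients were treated that way, the planned ratio compares all short-acting use on one side with part of it on the other.

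This is a difference in the outcome itself. Matching the charts or adjusting for baseline covariates would not remove it.

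What is at stake is the reading of the first of the three between-cohort efficacy measures. Section 3.c motivates the study partly by the lack of data on respiratory therapy utilization under short-acting regimens. A regimen that replaced scheduled treatments with a smaller number of on-demand ones could be reported as increasing the need for treatment.

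**Working it through.** The plan states no PRN rate, expected ratio, alpha or power for this comparison, so there is no figure to reproduce.

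**Inputs from the documents**
- Historical charts: 60. Short-acting only: 30%, so 0.30 × 60 = 18. LABA with PRN: 70%, so 0.70 × 60 = 42 (section 3.c).
- Guideline frequency of the short-acting regimen: 4 per day plus as needed (section 3.c). The frequency actually given is not stated.
- Scheduled short-acting doses in the study: 0 (section 5.2.4, as written).

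**Step 1: size of the omission.** Let s be the share of the cohort with scheduled doses at 4 per day. The uncounted amount is U = 4s per patient-day, treating shares of patients as shares of patient-days (equal mean stay across regimens is assumed).

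| s | U |
|---|---|
| 30% (all 18) | 1.2 |
| 20% | 0.8 |
| 10% | 0.4 |
| 0% | 0 |

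**Step 2: when the sign reverses.** Let H be the historical PRN rate and T the study rate. The PRN ratio is T/H and the total ratio is T/(H + U). The first is above 1 and the second below 1 exactly when H < T < H + U. This needs no assumed PRN rate.

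**Step 3: illustration with assumed rates.** Take historical PRN of 1.0 per day in the short-acting-only charts and 1.5 in the rest. Then H = 0.30 × 1.0 + 0.70 × 1.5 = 1.35 and, with U = 1.2, H + U = 2.55.

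| Study rate T | T/1.35 (PRN) | T/2.55 (total) |
|---|---|---|
| 1.2 | 0.89 | 0.47 |
| 1.5 | 1.11 | 0.59 |
| 2.0 | 1.48 | 0.78 |
| 3.0 | 2.22 | 1.18 |

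The two measures disagree only between 1.35 and 2.55. At T = 2.0 the total ratio depends on s: 2.0/2.15 = 0.93 at 20%, 2.0/1.75 = 1.14 at 10%, and 2.0/1.35 = 1.48 at 0%. At 10% or less there is no reversal at this study rate.

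**Step 4: what splitting by regimen shows.** Assume PRN rates of 0.5 (short-acting only), 1.5 (LABA with PRN) and 1.5 (study). Pooled H = 0.30 × 0.5 + 0.70 × 1.5 = 1.20, so the PRN ratio is 1.5/1.20 = 1.25. Against the LABA charts it is 1.5/1.5 = 1.00; against the short-acting-only charts it is 1.5/0.5 = 3.00. The total ratio is 1.5/2.40 = 0.63. The pooled excess comes entirely from the charts with scheduled doses.

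**Step 5: could the planned model report this as significant?** I simulated robust Poisson regression with a log patient-days offset, 60 against 80 patients, 1,000 runs and a two-sided 5% level. Assumptions: mean stay 4 days, gamma overdispersion with shape 1, and all 18 short-acting-only patients on four scheduled doses a day.

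| Assumed PRN rates (short-acting only / LABA / study) | PRN: study significantly worse | Total: study significantly better |
|---|---|---|
| 0.5 / 1.5 / 1.5 | 22% | 78% |
| 0.5 / 1.0 / 1.5 | 76% | 42% |
| 0.5 / 2.0 / 2.0 | 22% | 51% |

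No run gave a significant result in the opposite direction on either measure. These figures show that reversal is possible; they do not estimate how likely it is in this trial.

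**The case against.** The strongest reply is that section 3.c gives four times daily as what guidelines encouraged, in a sentence about how far practice departed from them. The charts come from an earlier analysis whose abstraction rules are not in these documents. If none of the 18 patients had scheduled doses, the bias is zero. That stands, and it is why the size is a range starting at zero.

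A reader might infer several stronger things that the documents do not support:

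- **That the short-acting-only patients were in fact on scheduled treatment and needed fewer PRN doses because of it.** Neither is stated. The second is plausible, but the reversal condition in step 2 does not depend on it.
- **That the whole historical cohort is non-comparable because its PRN treatments could include a SAMA.** The outcome is a number of treatments, and nothing shows that drug content would change that number. For the 70% on LABA, a PRN count is the natural comparator.
- **That every between-cohort efficacy measure is affected.** Length of stay and rehospitalization do not depend on how treatments are counted.
- **That the exploratory cost objective inherits the problem.** No section says that cost will be derived from PRN counts.
- **That total short-acting use should replace PRN use as the main between-cohort result.** Scheduled short-acting doses are zero in the study by design, so the total falls partly by construction, whatever the patient's need. It also leaves out the daily inhaler administration and any historical scheduled LABA or LAMA treatments. The primary objective concerns PRN requirements, so the PRN rate should stay.

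The objection does not supply a definition of a historical PRN treatment, a count of scheduled doses, or a split by regimen. The plan has none of these.

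**Conclusion.** The concern holds as a possibility that the plan neither measures nor excludes. It covers at most about 18 of the 60 historical charts, and the uncounted amount lies between 0 and 1.2 treatments per patient-day across the cohort. The upper end assumes that all 18 followed the guideline frequency.

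The bias has one direction: against the study regimen. A PRN result favouring the study could not be explained by it. An unfavourable one would mislead on total short-acting use only if the study rate lay between the historical PRN and total rates. All PRN rates, stays and dispersion used above are assumptions, so the ratios and percentages show direction only.

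This is a secondary comparison and the study's own PRN endpoint is untouched. It is still worth correcting before the analysis, because section 8.7.d presents the pooled PRN ratio as evidence of efficacy.

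**What to change.** In objective 5 and section 8.7.d(1), keep the PRN rate comparison and add the following:

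1. State one definition of a PRN treatment and apply it to both cohorts, including how a scheduled short-acting dose in a historical chart is classified.
2. Present the PRN rate ratio separately against the historical LABA-with-PRN charts (about 42, the like-for-like comparison) and the short-acting-only charts (about 18).
3. Add total short-acting treatments, scheduled plus PRN, per patient-day as a companion between-cohort result, with a note that scheduled short-acting doses are zero in the study by design.
4. State that no efficacy conclusion will be drawn from the pooled PRN ratio alone.

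**Cost.** Scheduled short-acting administrations must be re-abstracted from up to 60 existing charts if they are not already held, and the SAP wording revised. The subgroup comparisons will be less precise, especially the one with about 18 charts. The study CRF already provides for the number and time of SABA treatments, so no new patients, visits or procedures are needed.

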#### 4. PATIENT POPULATION

**a. Enrollment Goal**

This study aims to enroll 80 subjects. With an anticipated acceptance rate of 2/3, this means we will approach 120 eligible candidates over that period. We estimate we will be able to achieve 30-day follow-up in 80% of enrolled patients.

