#### **5.2.6 30 DAY POST DISCHARGE/WITHDRAWAL FOLLOW-UP**

Subjects will receive a follow-up phone call from a study coordinator and Medical Charts will be reviewed to assess if the subject was readmitted within 30 days of discharge. Follow-up phone call and Medical Chart review will instead occur 30 days after withdrawal for patients who are withdrawn prior to discharge.

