## **9. STATISTICAL ANALYSIS & DATA MANAGEMENT**

Continuous variables will be reported as means  $\pm$  standard deviations or medians [quartile 1, quartile 3], if skewed. Categorical variables will be reported as frequencies and percentages.

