### **b. Sample Size & Accrual Rate**

Enrollment of 80 patients.

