#### **e. Reporting and Exclusions**

Missing data will not be imputed or carried forward in any of the analyses.

The sample size for continuous variables will be the number of subjects with non-missing data; in the summary of categorical variables, subjects with missing data will be excluded in the calculation of percentages.

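### The comparison of readmission with the historical cohort yields a rank-test p-value but no planned difference or confidence interval; length of stay has the same gap

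*Combined protocol and SAP*

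**What the plan says.** The fifth secondary objective (section 2.b) is "To compare the number of PRN treatments, length of hospital stay, and rate of readmissions with findings in a previously" analysed "historical cohort of 60 patients in our healthcare system". Section 8.7.d presents this comparison as the assessment of the treatment protocol's efficacy and gives it three parts. PRN treatments per patient-day are estimated with a robust Poisson model. Length of stay and, as the last item, "3) the rate of rehospitalization, using the Wilcoxon Rank sum test" are compared by rank test.

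Readmission is recorded as yes or no: section 5.2.6 provides a phone call and a chart review "to assess if the subject was readmitted within 30 days of discharge". The first paragraph of section 8.7.d allows t-tests, chi-square, rank sum or Fisher's exact tests as appropriate, but only for comparing readmitted with non-readmitted patients inside the study cohort.

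On reporting, the introduction to the statistical section says "Categorical variables will be reported as frequencies and percentages", with means or medians for continuous variables. Section 8.7.b gives the sample size as "Enrollment of 80 patients", with no power, precision, significance level or margin.

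**The concern.** A rank test is meant for ordered or continuous data, so naming it for a binary outcome does not fit the rest of the section. That mismatch is the visible part of the problem, and the smaller part.

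This objective is the study's only planned comparison with previous care. With cohorts of this size, what matters is how large the difference is and how uncertain. The Poisson model for PRN treatments can supply a rate ratio with an interval. For readmission and length of stay the plan names a test and no measure of effect. If the p-value is large, the planned output would not show whether the data exclude an important change in either direction.

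**Working it through.** **Inputs from the documents**
- Study cohort: 80 enrolled (section 8.7.b).
- Patients with 30-day follow-up: section 4.a says "We estimate we will be able to achieve 30-day follow-up in 80% of enrolled patients", so 0.80 × 80 = 64. Section 8.7.e says "Missing data will not be imputed or carried forward in any of the analyses", so the readmission analysis could rest on 64.
- Historical cohort: 60 (section 2.b).

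**Assumptions (not in the documents)**
- Readmission rate 20% in both cohorts, range 10% to 30%.
- Two-sided 5% level and 95% intervals.
- All counts in the examples below.

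**Step 1: the plan's own figure.** The 80 has no statistical derivation to reproduce. Only the accrual arithmetic in section 4.a can be checked: 120 × 2/3 = 80, which agrees.

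**Step 2: is the rank-sum p-value wrong?** On 0/1 data the tie-corrected rank sum test without continuity correction equals the chi-square test with its statistic multiplied by (N−1)/N. Illustrative counts, study against historical:

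| Counts | Rank sum p | Pearson chi-square p | Fisher p | Smallest expected count |
|---|---|---|---|---|
| 13/64 vs 12/60 | 0.966 | 0.965 | 1.00 | 12.1 |
| 8/64 vs 16/60 | 0.047 | 0.046 | 0.068 | 11.6 |
| 6/64 vs 13/60 | 0.059 | 0.058 | 0.080 | 9.2 |
| 3/64 vs 9/60 | 0.053 | 0.052 | 0.070 | 5.8 |

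The rank-sum and chi-square p-values agree to about 0.001. Fisher's test gives a larger p-value in every row, and in the second row it falls on the other side of 0.05.

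**Step 3: can the rank statistic be read as an effect?** On binary data U/(n1 × n2) = 0.5 + (risk difference)/2. For 6/64 vs 13/60 the risk difference is 0.0938 − 0.2167 = −0.1229, and 0.5 − 0.0615 = 0.4385, which matches the rank statistic. An effect can therefore be recovered, but the plan does not ask for it.

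**Step 4: what would an interval show?** With equal rates p, the half-width is 1.96 × √[p(1−p)(1/n + 1/60)].
- p = 20%, n = 64: 1.96 × √[0.16 × (0.01563 + 0.01667)] = 14.1 points.
- p = 20%, n = 80: 1.96 × √[0.16 × (0.01250 + 0.01667)] = 13.4 points.

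| Assumed rate | 64 vs 60 | 80 vs 60 |
|---|---|---|
| 10% | 10.6 | 10.0 |
| 15% | 12.6 | 12.0 |
| 20% | 14.1 | 13.4 |
| 25% | 15.3 | 14.5 |
| 30% | 16.1 | 15.3 |

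**Step 5: one worked case.** For 13/64 (20.3%) vs 12/60 (20.0%) the difference is +0.3 points. The Wilson limits are 12.3% to 31.7% and 11.8% to 31.8%. Newcombe's method combines them:
- lower limit: 0.3 − √[(20.3 − 12.3)² + (31.8 − 20.0)²] = −14.0 points;
- upper limit: 0.3 + √[(31.7 − 20.3)² + (20.0 − 11.8)²] = +14.3 points (from unrounded values).

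The planned output would be two similar percentages and p = 0.97. The interval of −14.0 to +14.3 would not appear.

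**Step 6: could a difference of that size be missed?** Using the normal approximation for two proportions with 20% in the historical cohort, power for a fall to 6% is 65% (64 vs 60) or 70% (80 vs 60). For a rise to 34% it is 42% or 44%. A true 14-point difference could easily be non-significant.

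No similar calculation is possible for length of stay, because the documents give no spread for it.

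**The case against.** The strongest reply is that little turns on the choice of test. The p-value matches chi-square, the effect can be recovered from the rank statistic, and an exact version of the rank test on 0/1 data is equivalent to Fisher's test. All of that stands, and the point does not rest on the p-value being invalid.

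A reader might infer that the rank test is unsafe here when readmissions are few. The examples do not show this. In the two with fewest readmissions the smallest expected counts are 9.2 and 5.8, both above the usual threshold of 5, and neither the rank sum test nor Fisher's falls below 0.05. Fisher's test is conservative, so a smaller p-value than Fisher's is not in itself an error. The 8/64 vs 16/60 table shows that the choice between tests can decide the label, but chi-square gives the same label as the rank test.

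It can also be said that the plan already reports percentages, and means or medians for length of stay. If both cohorts are tabulated, a reader can subtract the percentages and even calculate an interval from the four counts. This stands in part: the raw material would exist, but no interval is planned.

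Finally, 64 may be pessimistic, because chart review supplements the phone call. With all 80 followed, the half-width at a 20% rate falls only from 14.1 to 13.4 points.

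**Conclusion.** The concern holds in a limited form. The named test does not fit the yes/no outcome and is inconsistent with the preceding paragraph, but its p-value is usable. The substantive gap is the absence of a planned between-cohort difference and interval for readmission and length of stay.

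For readmission, the uncertainty left unreported is about 10 to 16 points either side, over assumed rates of 10% to 30% and 64 to 80 study patients against 60. The figure of about 14 points needs an assumed rate near 20% with 64 analysed, and is not a figure from the documents.

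A reader might also infer that the plan will treat a non-significant result as showing equal readmission. The documents do not say so, and they plan no equivalence or non-inferiority claim. It is a risk of interpretation that attaches to any bare p-value at this sample size, whichever test is used.

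The weight is modest: two of the three outcomes under one secondary objective are affected, and the primary endpoint is not.

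**What to change.** In section 8.7.d, separate the two outcomes:
- **Rehospitalization:** report the number and proportion readmitted in each cohort, with denominators, and the risk difference with a Newcombe 95% confidence interval. For any p-value, name either the chi-square or Fisher's exact test before the data are analysed, because the two can disagree near 0.05.
- **Length of stay:** keep the rank sum test and add the Hodges-Lehmann difference with its 95% confidence interval.
- **Interpretation:** add a sentence that a non-significant result will not be taken as evidence of equal readmission.

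The change needs no new patients or data. It costs slightly more analysis work, and it will probably produce a wide interval that makes the comparison's limited precision visible.
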